	14	Someone to love and make you feel wanted
	15	Someone who hugs you
Positive social	16	Someone to have a good time with
interaction	17	Someone to get together with for relaxation
	18	Someone to do something enjoyable with
Additional item	19	Someone to do things with to help you get your mind off things

Raw scores for each subscale (emotional/informational, tangible, affectionate, positive social interaction) of the MOS-SSS as well as the total score will be calculated as follows:

- Tangible Support Subscale (TAN)
 - o ss tan raw bl, ss tan raw el: Sum items 9-12
 - o ss_tan_avg_bl, ss_tan_avg_el: Average items 9-12
- Emotional/Informational Support Subscale (EMI)
 - o ss_emi_raw_bl, ss_emi_raw_el: Sum items 1-8
 - o ss emi avg bl, ss emi avg el: Average items 1-8
- Affectionate Support Subscale (AFF)
 - o ss_aff_raw_bl, ss_aff_raw_el: Sum items 13-15
 - o ss_aff_avg_bl, ss_aff_avg_el: Average items 13-15
- Positive Social Interaction Subscale (POS)
 - o ss pos raw bl, ss pos raw el: Sum items 16-18
 - o ss pos avg bl, ss pos avg el: Average items 16-18
- Total Score
 - o ss_tot_raw_bl, ss_tot_raw_el:Sum items 1-19
 - o ss_tot_raw_chng: Δ BL to EL: total raw score, EL total raw score, BL
 - o ss_avg_bl, ss_avg_el:Weighted average:(ss_tan_avg + ss_emi_avg + ss aff avg + ss pos avg + item 19)/5
 - o ss avg chng: Δ BL to EL, ss avg_el ss_avg_bl

The confirmatory factor analysis will inform which approach to score generation we present and use in the final analyses.

Social Isolation [PROMIS Social Isolation 4a]²

For this abbreviated, 4-item instrument, raw scores will be created by summing all four items. Conversion tables will be used to convert the raw score to a T-score for each participant.

ltem no.	Item	Never	Rarely	Sometimes	Usually	Always
1	I feel left out	1	2	3	4	5
2	I feel that people barely know me	1	2	3	4	5
3	I feel isolated from others	1	2	3	4	5
4	I feel that people are around me but not with me	1	2	3	4	5

Depression [PHQ-8]³

The PHQ-8 asks respondents on how many days over the prior two weeks they experienced 8 possible symptoms, with response options of "not at all"=0, "a few days"= 1, "more than half the days"=2, and "most all of the days"=3. The score for each item is summed and a total score that ranges from 0 to 24 is assigned. Respondents who score 10-19 points are considered to have major depression and those who score 20 or more have severe depression.⁴

Over t	Over the last 2 weeks, how often have you been bothered by any of the following problems?				
ltem no.	Item	Not at all	A few days	More than half the days	Most all of the days
1	Little interest or pleasure in doing things	0	1	2	3
2	Feeling down, depressed, or hopeless	0	1	2	3
3	Trouble falling or staying asleep, or sleeping too much	0	1	2	3
4	Feeling tired or having little energy	0	1	2	3
5	Poor appetite or overeating	0	1	2	3
6	Feeling bad about yourself, or that you are a failure, or have let yourself or your family down	0	1	2	3
7	Trouble concentrating on things, such as reading the newspaper or watching television	0	1	2	3
8	Moving or speaking so slowly that other people could have noticed. Or the opposite – being so fidgety or	0	1	2	3

² Information on scoring the PROMIS Social Isolation instrument is available from: chrome-

http://patienteducation.stanford.edu/research/phq.pdf.

extension://oemmndcbldboiebfnladdacbdfmadadm/http://www.healthmeasures.net/images/PROMIS/manuals/PROM IS Social Isolation Scoring Manual.pdf

³ Information on PHQ-8 scoring is available from: http://patienteducation.stanford.edu/research/phq.pdf and chrome-

extension://oemmndcbldboiebfnladdacbdfmadadm/https://www.selfmanagementresource.com/docs/pdfs/English_-_phq.pdf ⁴ PERC S. Personal Health Questionnaire Depression Scale (PHQ-8). [Internet]. 2013;

Analysis Plan: Using Social Media to improve ART Retention and Treatment outcomes among youth living with HIV in Nigeria - The Youth SMART study

restless that you have been moving around a lot more		
than usual		

Depression will be evaluated through the adolescent survey through the items of the PHQ-8. The PHQ-8 asks respondents on how many days over the prior two weeks they experienced 8 possible symptoms, with response options of "not at all"=0, "a few days"= 1, "more than half the days"=2, and "most all of the days"=3. The score for each item is summed as follows:

- Total score: Sum q605-612
- Δ BL to EL: total raw score, EL total raw score, BL

For pre-post comparison, we will present the mean and standard deviation of the scores at each time point. We will also descriptively present the percentage of participants who fall into each category below at each time point:

- Not depressed (variable=0) if total score <10
- Major depression (variable=1) if total score 10-19
- Severe major depression (variable=2) if total score ≥20

HIV-related stigma [HIV Stigma Scale-12 items]⁵

The abbreviated version of the HIV Stigma Scale has four sub-scales: Personalized stigma, disclosure concerns, concerns about public attitudes, negative self-image; each of these items is scored on a 4-point scale (1-4). A raw score will be generated for each sub-scale by summing the following items:

Next I'd like to ask you some questions about how you feel about having HIV and sharing that information with other people.

		-			
Factor	Item	Item			
Personalized stigma	1	214. Some people avoid touching me once they know I have HIV			
	2	5. People I care about stopped calling after learning I have HIV			
	3	216. I have lost friends by telling them I have HIV			
Disclosure concerns	4	217. Telling someone I have HIV is risky			
	5	218. I work hard to keep my HIV a secret			
	6	219. I am very careful who I tell that I have HIV			
Concerns about	7	220. People with HIV are treated like outcasts			
public attitudes	8	221. Most people believe a person who has HIV is dirty			
	9	222. Most people are uncomfortable around someone with HIV			
Negative self-image	10	223. I feel guilty because I have HIV			
	11	224. People's attitudes about HIV make me feel worse about myself			
	12	225. I feel I'm not as good a person as others because I have HIV			

Analysis Plan: Using Social Media to improve ART Retention and Treatment outcomes among youth living with HIV in Nigeria - The Youth SMART study

⁵ Scoring information available from:

https://www.ncbi.nlm.nih.gov/pmc/articles/PMC5450123/pdf/12955_2017_Article_691.pdf

Possible scores for each sub-scale range from 3 to 12. A greater score indicates a greater level of perceived HIV-related stigma. A total score will also be created by summing all 12 items. Changes in the total score from baseline to endline will also be calculated.

The confirmatory factor analysis will inform the approach to score generation we present and use in the final analyses.

Alcohol use risk [AUDIT-C]

The AUDIT-C is an abbreviated version of the 10-item Alcohol Use Disorders Identification Test (AUDIT) tool developed by the World Health Organization to measure harmful and hazardous alcohol drinking behaviors. For the AUDIT-C, each of the three items is scored on a 5-point scale (0-4), and the scores are totals across items for a final score that ranges from 0 to 12. A score of 3 or greater for women or a score of 4 or greater for men is indicative of harmful alcohol use.

Item no.	Item	Response options
Q601 [item 1]	How often do you have a drink containing alcohol?	0 =Never
		1=Monthly or less
		2=2 to 4 times a month
		3=2 to 3 times a week
		4=4 or more times a week
Q602 [item 2]	How many drinks containing alcohol do you have on a typical day when you are drinking?	0=1 or 2
		1=3 or 4
		2=5 or 6
		3=7, 8, or 9
		4=10 or more
Q603 [item 3]	How often do you have six or more drinks containing alcohol on	0=Never
	one occasion?	1=Less than monthly
		2=Monthly
		3=Weekly
		4=Daily or almost daily

Risky alcohol use will be measured by administering the AUDIT-C⁶ in the survey (q601-q603) and will be scored and categorized following AUDIT-C scoring guidelines:

• Total score=q601+q602+q603

Risky alcohol use will be denoted as an ordinal created variable following AUDIT-C guidelines:

- Males, age 29 and younger
 - Total score 8-12: Severe risk (variable=3)
 - Total score 6-7: High risk (variable=2)
 - Total score 4-5: Moderate risk (variable=1)
 - Total score 0-3: Low risk (variable=0)
- Females, age 29 and younger

Analysis Plan: Using Social Media to improve ART Retention and Treatment outcomes among youth living with HIV in Nigeria - The Youth SMART study

⁶ https://www.hepatitis.va.gov/provider/tools/audit-c.asp

- Total score 8-12: Severe risk (variable=3)
- Total score 6-7: High risk (variable=2)
- Total score 3-5: Moderate risk (variable=1)
- Total score 0-2: Low risk (variable=0)

AUDIT-C scoring guidelines specify that participants missing one or more response to the three items should be excluded from calculation of a total score; however, participants who respond "never drank alcohol" to q601 will be included with a total score of 0.

Food insecurity [HHS]⁷

Food insecurity will be measured using the FANTA project 3-item Household Hunger Scale. This tool was developed for use in LMIC settings that is capable of measuring food insecurity in a comparable way (i.e. cross-cultural equivalency). The abbreviated 3-item version of the scale asks if participants had experienced any of the following within the past 30 days, and if yes, how frequently:

- Was there ever no food to eat of any kind in your house because of lack of resources to get food
 - [if yes] How often did this happen? (Rarely [1-2 times], Sometimes [3-10 times], Often [more than 10 times])
- Did you or any household member go to sleep at night hungry because there was not enough food
 - [if yes] How often did this happen? (Rarely [1-2 times], Sometimes [3-10 times], Often [more than 10 times])
- Did you or any household member go a whole day and night without eating anything at all because there was not enough food
 - [if yes] How often did this happen? (Rarely [1-2 times], Sometimes [3-10 times], Often [more than 10 times])

Following scoring guidelines, a new variable will be created for each question with the following response options:

- Indicated that this type of food insecurity did not happen (variable=0)
- "Rarely" or "sometimes" (variable=1)
- "Often" (variable=2)

An aggregate score will be created by summing the three new variables. The aggregate score will have a minimum score of 0 and a maximum score of 6. Results at each time point will be represented as mean aggregate score at each time point. We will also present the proportion of participants in each of the following household hunger categories as per the HHS scoring guide:

- Aggregate score 0-1: Little to no hunger in household
- Aggregate score 2-3: Moderate hunger in household
- Aggregate score 4-6: Severe hunger in household

Adherence

Adherence will be dichotomized at baseline and endline (adh_bl,adh_el) based on self-reporting having missed one more medication dose in the past 3 days (q422).

Code:

gen adh_el=.

⁷ Information on scoring the HHS is available from: https://www.fantaproject.org/sites/default/files/resources/HHS-Indicator-Guide-Aug2011.pdf

replace adh_el=1 if if q420==1 | q420==2 | q420==3 | q421==1 | q421==2 | q421==3 | q422==1 | q422==2 | q422==3 | q422==4 | q422==5; 0 otherwise

replace adh_el=0 if adh_el==. & (q420==4 | q420==5 | q420==6 | q421==0 | q422==0)

VL suppression

A dichotomous variable, vl_sup, will be created for each VL measurement instance to indicate virologic failure following the standard definition of virologic suppression being <1,000 cp/mL. The variable will be missing for any instances where VL measures were not available.

HIV knowledge and treatment literacy

HIV knowledge and treatment literacy will be assessed using a set of fifteen true/false questions [q226 – q240] administered at baseline, midpoint, and endline. For each knowledge question, a new variable will be created to more easily quantify correct responses and will be coded as 1 if a correct response was given, and 0 if an incorrect answer, "don't know" response, or refusal was given. For example:

q226 re=1 if q226=1, q226 re=0 if q226=0 | q226=8 | q226=99

At each timepoint, knowledge will be quantified as follows:

know=sum(q226_re-q240_re)/15*100

Changes in knowledge scores from baseline to endline will be quantified as follows:

```
know_chng=know_el - know_bl
```

Responsiveness to particular questions as well as changes from baseline to midpoint, and midpoint to endline, will also be assessed descriptively.

Time on ART

Time on ART at baseline, art_time_bl, will be created based off of medical record data reporting the date the participant started ART as well as the date the participant conducted their baseline questionnaire.

art time bl =q011(from MRE)-today bl (from BL questionnaire)

V. Analysis of participant characteristics

Data from the baseline questionnaire will be cleaned and analyzed descriptively prior to the second round of data collection. Descriptive statistics including means and frequencies will be generated for all quantitative variables collected at baseline in addition to aggregate scores for multiple items measuring potential outcomes such as ART adherence and self-efficacy, social support, retention in HIV services, HIV-related stigma, depression/anxiety, and substance use. A descriptive summary of participant characteristics will be presented by intervention and control groups at all time points. Participant characteristics will include age, marital/relationship status, education, religious affiliation, employment, and food insecurity/household hunger.

VI. Analysis of Study Objectives

Objective 1.

To test the effect of the intervention on the primary outcome, retention in care, we will report Kaplan-Meier cumulative retention probabilities with 95% confidence intervals and plots by study group. The retention probabilities between the groups will be compared with a logrank test stratified by site with a two-sided alpha = 0.05.

The null hypothesis is:

YLHIV who participate in SMART Connections will have the same likelihood of being retained in HIV care at 270 days as YLHIV in the control group.

The alternative hypothesis is:

YLHIV who participate in SMART Connections will be more likely to be retained in HIV care at 270 days than YLHIV in the control group.

Data will be prepared using the stset command:

```
stset timevar, id(id_str) failure(ltfu_28=1) origin(time -0.01) exit(time
```

270)

Where:

```
timevar - time to failure in days, created variable ret_time_28 defined
above
idvar - participant ID id_str
failvar - failure variable, created ordinal variable ltfu 28 defined above
```

The origin command includes participants with 0 survival time because these participants had the potential to be retained in care during the study period. The exit command specifies that 270 days is the latest timepoint at which we will assess retention.

Kaplan-Meier cumulative retention probabilities at endline with 95% confidence intervals, by study group:

sts list, by(group_itt) ci

Plots by study group:

sts graph, by(group_itt) ci

Log-rank test for difference in retention between groups , stratified by site:

sts test group, strata(facility) detail

Secondarily, we will also conduct the survival analysis described above using the 90 day cutoff variables (i.e. ltfu_90, ret_time_90).

We will also report on the proportion of participants, by study arm, who are retained at 12 months after enrollment. We will use additional regression models (For example, a multivariate Cox proportional hazards model) to explore factors associated with retention in further detail, such as time on ART at enrollment, age, and sex.

If the variables other than retention included in these models have ≥5% missingness, a multiple imputation model will be run as a secondary analysis. Multiple imputation creates multiple sets of plausible values for missing data that reflect the uncertainty about the missing data. The imputation model will include additional variables that are theoretically related to the variables being imputed (Chantala & Suchindra; Stuart, 2009; White, 2011): Age, sex, date of HIV test, date of ART initiation, depression, and social support. We will impute individual items (for example, individual items missing from the social support measure), rather than generated scores. Although there is some controversy as to whether to round categorical variables after imputation (Allison, 2005), we will round the values in each variable in order to facilitate interpretation of results and given expected very small proportion of missing data.

The multiple imputation procedure involves 3 phases (Rubin, 1996; Yuan, 2000):

- 1. The missing data are filled in m times to generate m complete data sets.
- 2. The m complete data sets are analyzed by using standard procedures.

3. The results from the m complete data sets are combined for inference.

Two main assumptions underlie the multiple imputation procedure. First, the data are assumed to be missing at random (MAR). According the SAS User Guide (2003a), for a variable to be MAR, "the probability that an observation is missing can depend on the observed variable values of the individual, but not on the missing variable values of the individual." Although the MAR assumption cannot be verified, since independence from the missing values cannot be estimated, Schafer states that the assumption becomes more plausible as the number of variables included in the imputation model increases (Schafer, 1997). We will assess MAR and verify that there is no reason to think the missing-at-random assumption is violated using the mi misstable patterns command specified for the variables to be included in the multiple imputation. The second assumption is that of multivariate normality. However, according to Schafer (1997), inferences based on multiple imputation can be robust to departures from the assumption if the amount of missing data is not large.

The mi set of commands (mi set, mi impute, and mi estimate) will be used for the multiple imputation procedure. To allow results to be reproducible, a random-number seed will be set. M=10 imputed datasets will be created.

For participants that have complete medical record for the study period (i.e. conservative=1, ltfu 28!=. and ret time 28!=0), we will also descriptively present the following by ITT intervention arm:

- n visits=number of clinic visits attended during the study period
- n missed 28=Number of clinic visits missed by more than 28 days during the study period •
- mean followup mo=Mean months of follow-up time during the study period ٠

Objective 2.

To examine the association between treatment exposure and secondary outcomes of social support, HIV knowledge and treatment literacy, adherence and viral suppression, we will conduct significance testing using two-sided tests, with an alpha of 0.05. To examine the relationship between treatment exposure and social support, a continuous variable, we will conduct a t-test using treatment exposure (group) and change from baseline to endline in social support score (ss avg chng). We will similarly examine the relationship between treatment exposure and HIV knowledge by conducting a t-test using treatment exposure (group) and change from baseline to endline in total knowledge score (know chng).

For adherence and viral suppression at endline, both of which will be dichotomized, we will conduct chisquare tests. We will also explore associations between treatment exposure and secondary outcomes using multiple linear regression models:

1. Social support

Model:	Multiple Linear Regression
Outcomes:	Change in social support score from baseline to endline (ss_avg_chng, individual sub- scales)
Exposures:	Study group (intervention v. comparison)
Covariates:	Age, sex, education at baseline, depression score at baseline, social isolation score at baseline

2. HIV knowledge/treatment literacy

Multiple Linear Regression Model:

Analysis Plan: Using Social Media to improve ART Retention and Treatment outcomes among youth living with HIV in Nigeria - The Youth SMART study

Outcomes: Change in knowledge score from baseline to endline (know chng)

Study group (intervention v. comparison) Exposures:

Covariates: Age, sex, education at baseline

3. Self-reported adherence

Model:	Multiple Logistic Regression
Outcomes:	Adherence at endline
Exposures:	Study group (intervention v. comparison)
Covariates:	Age, sex, education at baseline, household hunger score at baseline, time on ART at baseline, social support sub-scales, adherence at baseline

4. Viral load

Model:	Multiple Linear Regression
Outcomes:	Viral load at endline
Exposures:	Study group (intervention v. comparison)
Covariates:	Age, sex, education at baseline, household hunger score, adherence, time on ART at baseline, social support sub-scales

We will check that the following assumptions of multiple regression are met:

- Independence of observations (i.e. independence of residuals) ٠
- Linear relationships between dependent variable and each independent variable, and between dependent variable and the independent variables collectively. Method: Scatterplots
- Homoscedasticity variance does not change along line of best fit. Method: Plotting studentized • residuals against unstandardized predicted values
- No multicollinearity. Method: Inspect correlation coefficients and VIF values •
- No significant outliers, highly influential points, etc. Method: Exploratory data analysis
- Normal distribution of residuals. Method: Histogram with normal curve fitted, and normal p-plot of residuals

If any of the variables specified above have \geq 5% missingness, a multiple imputation model will be run as a secondary analysis. The imputation model will include additional variables that are theoretically related to the variables being imputed (Chantala & Suchindra; Stuart, 2009; White, 2011):

Model 1: Age, sex, education at baseline, depression scores, social isolation scores

Model 2: Age, sex, education at baseline

Model 3: Age, sex, education at baseline, household hunger score at baseline, social support sub-scales

Model 4: Age, sex, education at baseline, household hunger score, adherence, social support sub-scales

Although there is some controversy as to whether to round categorical variables after imputation (Allison, 2005), we will round the values in each variable in order to facilitate interpretation of results and given expected very small proportion of missing data.

The multiple imputation procedure involves 3 phases (Rubin, 1996; Yuan, 2000):

- 1. The missing data are filled in m times to generate m complete data sets.
- 2. The m complete data sets are analyzed by using standard procedures.
- 3. The results from the m complete data sets are combined for inference.

The mi set of commands (mi set, mi impute, and mi estimate) will be used for the multiple imputation procedure. To allow results to be reproducible, a random-number seed will be set. M=10 imputed datasets will be created.

Objective 3.

For the third objective, to examine the potential mediating effect of social support on the relationship between the intervention and the primary outcome, retention in care, we will use the Barron and Kenney approach. Kenney and colleagues describe a 4-step strategy for testing mediation, which includes:

- 1. Establish a statistically significant relationship between the independent variable (intervention) and the dependent variable (retention in care)
- 2. Establish a statistically significant relationship between the mediator (social support) and the independent variable (intervention)
- 3. Establish a statistically significant relationship between the mediator (social support) and the dependent variable (retention in care)
- 4. Demonstrate that the relationship between the independent variable and the dependent variable is significantly reduced when the mediator is added to the model. The significance of the mediated effect can be assessed using a statistical procedure known as the Sobel test ⁵⁸.

The hypothesis is:

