This main outcome is defined as retention in clinical HIV services and on treatment, defined as having attended a scheduled HIV clinic visit within 4 weeks of the visit date. To be considered retained in HIV services at endline, an individual must, at endline, have picked up his/her medication for his/her most recently scheduled clinical follow-up visit within 4 weeks (28 days) of the date when it was scheduled to take place. "Endline" will be considered the date of the participant's endline interview, or, for those that did not participate in an endline interview, an approximate date based on the median length of time between baseline and endline for other participants enrolled in the same month. We will record, from the medical record, if a participant has knowingly enrolled in services elsewhere (transferred), in which case attempts to contact the participant will be made, if feasible; we will also record if the participant has died, defaulted, or has been recorded as lost to follow-up.

Cases that can be confirmed to have died or transferred to a facility outside the study facilities and retention data cannot be obtained reliably will be considered censored.

Nigeria's definition of retention in HIV services changed during the course of the study, to be more stringent (4 weeks vs. 12 weeks). We will therefore secondarily assess retention using the older, less stringent, definition.

Created variables will be defined as follows:

Analysis Plan: Using Social Media to improve ART Retention and Treatment outcomes among youth living with HIV in Nigeria - The Youth SMART study PHSC #1151489; Version 1.0; December 2019

ltfu_el - care status at EL

0=in care at EL

Latest visit (i.e. v5q036) +/- 28 days from today_el/today_el_approx actual visit (i.e. v5q036) more than 28 days before today_el/today_el_approx AND follow-up visit (i.e. v3q044) on or after today_el/today_el_approx

1=LTFU at EL

actual visit < today_el/today_el_approx + 28 days AND latest MRE on or after today el/today el approx

8=Transfer

transfer==1 AND q027 is before today_el/today_el_approx AND q027 is AFTER
the latest visit (i.e. v3q036)

9=Death

death == 1

.=Missing

Insufficient data to assess care status at endline. latest_mre is before today_el/today_el_approx AND latest follow-up date (i.e. v1q044) before today_el/today_el_approx

Retention for survival analysis

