For the survival analysis, we will create two sets of variables indicating retention using a 28 day cutoff and using a 90 day cutoff to reflect the fact that the national guidelines for retention in HIV services changed from 12 weeks (i.e. 90 days) to 4 weeks (i.e. 28 days). For each recorded visit, we will also assess whether the participant is within their scheduled window and the number of days between the scheduled visit date and the date the visit was actually attended (v1 denotes the first attended visit after study enrollment; v2, v3, v4, etc. will be calculated for all visits between study enrollment and date of EL questionnaire (or date EL questionnaire should have been conducted, based on enrollment date, for those LTFU in the study at endline):

For each visit, starting at visit 2 (i.e. v2):

- v2_days_aftersched = [visit date (v2q036)] [date of prior scheduled visit (v1q044)]; missing if either date is . or jan 1 1990
- v2_ltfu_28 = 1 if v1_days_aftersched >28; = 0 if v1_days_aftersched ≤28; missing if next scheduled visit date (v1q044) is missing (. or jan 1 1990).
- v2_ltfu_90 = 1 if v1_days_aftersched >90; = 0 if v1_days_aftersched ≤90; missing if next scheduled visit date is missing (. Or jan 1 1990).

1tfu 28 LTFU status for survival analysis using 28 day cutoff

- **ltfu_28**=1; lost to follow-up
 - o v2 ltfu 28==1 OR v3 ltfu 28==1 OR v4 ltfu 28==1, etc.
 - o Appears retained for all recorded visits, but earliest value of today_el, today_el_approx, latest_mre falls MORE than 28 days after latest instance of vnq044
- ltfu 28=0; retained

- o v2 ltfu 28==0 AND v3 ltfu 28==0 AND v4 ltfu 28==0, etc. AND the earliest value of today el, today el approx, latest mre falls within 28 days of latest instance of **vnq044**
- 1tfu 28=8; transferred out
 - o Retained up to the date of transfer (transfer==1 and q027, transfer date, must be non-missing)
- **ltfu 28**=9; died
 - o Retained up to the date of death (death==1 and q028, death date, must be non-missing)

1tfu 90 LTFU status for survival analysis using 90 day cutoff

- **ltfu 90**=1; lost to follow-up
 - o v2 ltfu 90==1 OR v3 ltfu 90==1 OR v4 ltfu 90==1, etc.
 - o Appears retained for all recorded visits, but earliest value of today el, today el approx, latest mre falls MORE than 90 days after latest instance of **vnq044**

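### Retention at endline (`ltfu_el`) is not coded from the scheduled visit date as the SAP's own definition requires, and the Objective 3 models are inconsistently specified; secondary analyses only

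*SAP*

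**What the plan says.** **SAP IV.C, Retention at endline.** The written definition requires that, at endline, medication was collected for the "most recently scheduled clinical follow-up visit within 4 weeks (28 days) of the date when it was scheduled to take place". The coding of `ltfu_el` that follows reads:

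- Code 0 (in care) has two routes, which must be alternatives because no visit can satisfy both. The first is "Latest visit (i.e. v5q036) +/- 28 days from today_el/today_el_approx". The second is a last visit more than 28 days before endline with the next appointment on or after endline.
- Code 1 (lost) is "actual visit < today_el/today_el_approx + 28 days AND latest MRE on or after" the endline date.
- Code 8 (transfer) carries date limits. Code 9 (death) is the death indicator alone.
- Missing applies when the records cannot settle the status: "latest_mre is before today_el/today_el_approx AND latest follow-up date (i.e. v1q044) before" endline.

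**SAP IV.C, Retention for survival analysis.** `ltfu_28` works from the scheduled date (`vnq044`). Visit variables "will be calculated for all visits between study enrollment and date of EL questionnaire" or its planned date. Someone with no late visit is still lost if the earlier of endline and the last record date "falls MORE than 28 days after latest instance of vnq044". Death needs "Retained up to the date of death (death==1 and q028, death date, must be non-missing").

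**SAP VI.** Objective 1 runs the log-rank test on `ltfu_28` and `ret_time_28`. Objective 3 uses `ret_el` as outcome and `ss_tot_chng` as mediator. Objective 4 divides cost by the number assigned to a Facebook group and retained at endline.

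**The concern.** The words and the code for one outcome use different anchors: the words use the scheduled date, while the code mainly uses the endline date. If the code is followed, a very late return can count as retention, and one report could show the same person as lost in the survival analysis and in care in the mediation or cost analysis.

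`ltfu_el` is the only variable defined under the endline heading, so it presumably feeds Objectives 3 and 4, although the SAP does not say so. In Objective 3 the outcome variable, the mediator score and the model form would also have to be settled after data are seen.

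**Working it through.** **Set-up.** Day 0 is endline. Earlier visits are taken as on time. Codes are taken in listed order, each filling only empty values, which is the reading most favourable to code 1.

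**Person 1: due day -52, returns day +28, records to day +28.**
- Lateness: 28 - (-52) = 80 days.
- Written definition: 80 > 28, not retained.
- `ltfu_el`: the latest visit is 28 days from endline, so the first route is met and the code is in care.
- `ltfu_28`: 0 - (-52) = 52 > 28, lost. If the late return were counted, 80 > 28 gives the same answer.

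More generally, anyone more than 28 days overdue at endline who returns on days +1 to +28 is in care on `ltfu_el` and lost on `ltfu_28`, with no cap on lateness. For a due date of -52, lateness runs from 1 + 52 = 53 to 80 days.

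**Code 1 as printed.** A person seen on time on day -5 meets code 0 (5 ≤ 28) and also code 1 (-5 < +28, records to endline). Reading the sign as minus 28 removes this overlap, since -5 is not below -28. It leaves Person 1 in care, because code 0 still holds.

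**Person 2: last seen day -40, due day -10, records to endline, no return.**
- `ltfu_el`: 40 > 28, so the first route fails; -10 is before endline, so the second fails; code 1 applies, lost.
- `ltfu_28`: 0 - (-10) = 10 ≤ 28, retained.
- Written definition: open. Nothing had been collected at endline, but 28 - 10 = 18 days of the window remained.

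With records ending at endline and visit intervals of 28 days or more (the protocol's Measures section describes visits as usually monthly), everyone 1 to 28 days overdue splits this way: the last visit is at least 1 + 28 = 29 days back. At an assumed 14-day interval it holds for days 15 to 28.

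**Transfer order.** With a transfer on day -20, last visit on day -50, next appointment due before endline and records to endline, code 1 is met before code 8 is reached.

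**Objective 3, set against the created variables.**
- `ret_el` is never created. If it copies `ltfu_el`, 0 means in care, so even its direction is unstated.
- `ss_tot_chng` is never created. Section IV.C creates `ss_tot_raw_chng` and `ss_avg_chng`; Objective 2 uses the latter. They weight items differently: item 19 carries 1/19 = 5.3% of the raw total and 1/5 = 20% of the average (3.8 times as much); the eight emotional/informational items carry 8/19 = 42.1% against 20%.
- Steps 2 to 4 include pre/post time and, in each, a time interaction. The outcomes are a change score or one endline status, so each person has one record and time cannot vary.
- Step 3 is logistic in its heading and linear in its Model row. Step 4 is logistic, but the `medeff` and `medsens` templates fit the outcome with `regress`.
- Steps 1 to 3 adjust for sex; Step 4 does not.

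**The case against.** **Person 2 as a breach of the written rule.** A reader might infer this. The documents do not support it: the definition asks for collection by endline, so coding this person as lost fits one fair reading. If the person never returns and records run to day +60, `ltfu_el` agrees with the words and `ltfu_28` does not. What stands is a conflict between two SAP definitions that must be reconciled.

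**All disagreement between the variables as error.** This is also too strong. `ltfu_28` records any lapse; `ltfu_el` records status at endline. Someone due on day -80 who returns on day -20 is 60 days late and can be lost on one and in care on the other, partly by design. The protocol's analysis section plans to describe lapses and returns. Person 1 is different, because the return comes after endline and far outside the window.

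**The Missing code as a second overlap.** Someone seen on day -10, due on day -2, with records to day -5, meets both Missing and code 0 as printed. In listed order code 0 is filled first, so this is not pressed. The printed plus sign in code 1 may itself be an extraction fault and is weak evidence alone.

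**Exposure in Objective 3.** Endline interviews are normally held at a clinic appointment, the mediator needs the endline questionnaire, and the main analysis is complete-case. Many discordant people will therefore drop out of it. Telephone or off-site interviews and the secondary imputation leave some exposure. Objective 4 has no such filter.

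**Drafting slips.** Much of the Objective 3 list is of this kind: the commands are placeholders, `ss_tot_raw_chng` is the only created change score with a matching stem, and factor analysis is already meant to guide scoring. Even so, the SAP never says what replaces the placeholders. The omission of sex is minor, since Step 4 estimates mediation directly, but its heading also relies on the group effect shrinking.

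**Conclusion.** The point holds for secondary analyses and should be corrected. `ltfu_el` does not implement the SAP's 28-days-from-schedule rule: its first in-care route never tests lateness, and its lost code uses no scheduled date. Reading code 1 as residual or as minus 28 does not cure this. The death code has no date limit. For people still inside the window at endline, the two SAP definitions disagree and the words do not decide between them. Objective 3 rests on uncreated names, time terms that cannot be estimated and conflicting model forms.

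The documents do not give the number affected, and no direction of bias is claimed. The link from `ltfu_el` to Objectives 3 and 4 is an inference.

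A reader might infer that the primary result is at risk. These defects do not reach it, because the log-rank test uses `ltfu_28` and `ret_time_28`. That does not certify the primary coding: for example, `v2_ltfu_28` is set from a visit-1 day count although day counts are defined from visit 2 on, which is a separate matter.

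**What to change.** **Retention at endline.**
- Recode `ltfu_el` from the scheduled date (`vnq044`) of the most recent appointment due on or before endline, with the SAP's 28 days' grace.
- State, and reconcile with the survival definition, how to code (a) a person still inside the window at endline or when records end, (b) a return more than 28 days late but on or before endline, and (c) a missing `vnq044`, in line with the SAP's existing missing-date rules.
- Assign transfer and death before the residual lost code, limit death to deaths on or before endline, and use Missing only when records cannot settle the status.

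**Objectives 3 and 4.**
- Define `ret_el` from `ltfu_el` with its direction, for example `ret_el` = 1 if `ltfu_el` = 0 and `ret_el` = 0 if `ltfu_el` = 1, and name it in both objectives.
- Name one created social support change score as mediator, consistent with Objective 2 and the factor-analysis rule.
- Delete the time and time-interaction terms.
- Use one binary-outcome model for retention in Steps 1, 3 and 4, `medeff` and `medsens`, with the same covariates in Steps 1 and 4. If the sensitivity analysis needs another link because rho is a correlation of error terms, say so and use that link throughout.

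**Cost.** SAP wording and a few lines of code, using dates already abstracted. No new data and no change to the primary test.
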